**Statistical Analysis Plan:**

2.0 / 09-Jun-2023

Table 14.2-1.1.2 – Best Overall Response and Overall Response Rate  
Per Protocol Set

**PROGRAMMING NOTES:**

- Repeat Table 14.2-1.1.1
- Present data on Per Protocol Set.
- For Part B only

Table 14.2-1.1.3 – Best Overall Response and Overall Response Rate  
Evaluable Analysis Set

**PROGRAMMING NOTES:**

- Repeat Table 14.2-1.1.1
- Present data on Evaluable Analysis Set.

Table 14.2-1.2.1 - Overall, Target and Non-Target Lesion Response  
Full Analysis Set

	Group 1 N=XX n (%)	Group 2 N=XX n (%)	Group 3 N=XX n (%)	Group 4 N=XX n (%)	Group 5 N=XX n (%)	Group 6 N=XX n (%)	Overall N=XX n (%)
C1D28							
Target Lesion Response - n (%)							
Complete response (CR)	XX (XX.X)						
Partial response (PR)	XX (XX.X)						
Stable disease (SD)	XX (XX.X)						
Progressive disease (PD)	XX (XX.X)						
Not evaluable (NE)	XX (XX.X)						
Non-Target Lesion Response - n (%)							
Complete response (CR)	XX (XX.X)						
Non-Complete Response/Non Progressive Disease	XX (XX.X)						
Progressive disease (PD)	XX (XX.X)						
Not Applicable	XX (XX.X)						
Overall Response - n (%)							
Complete response (CR)	XX (XX.X)						
Partial Response (PR)	XX (XX.X)						
Stable Disease (SD)	XX (XX.X)						
Progressive disease (PD)	XX (XX.X)						
Not Evaluable (NE)	XX (XX.X)						

*Programming Note: Repeat for all  
available assessments*

Program: (Program name.sas) (run on: DDMMYYYY HH:MM)

Filename: (Specify file name.rtf)

**Sponsor:** BioMed Valley Discoveries

**Protocol:** BVD-523-ABC

**Statistical Analysis Plan:**

2.0 / 09-Jun-2023

Table 14.2-1.2.2 – Overall, Target and Non-Target Lesion Response  
Per Protocol Set

**PROGRAMMING NOTES:**

- Repeat Table 14.2-1.2.1
- Present data on Per Protocol Set.
- For Part B only

Table 14.2-1.2.3 – Overall, Target and Non-Target Lesion Response  
Evaluable Analysis Set

**PROGRAMMING NOTES:**

- Repeat Table 14.2-1.2.1
- Present data on Evaluable Analysis Set.

**Sponsor:** BioMed Valley Discoveries

**Protocol:** BVD-523-ABC

**Statistical Analysis Plan:**

2.0 / 09-Jun-2023

BioMed Valley Discoveries  
Protocol: BVD-523-ABC ('Delivery' / 'Type') - Part X  
Data extraction date: DDMMYYYY

Page 1 of Y

Table 14.2-1.3.1 - Incidence of New Lesions  
Full Analysis Set

	Group 1 N=XX n (%)	Group 2 N=XX n (%)	Group 3 N=XX n (%)	Group 4 N=XX n (%)	Group 5 N=XX n (%)	Group 6 N=XX n (%)	Overall N=XX n (%)
C1D28							
New Lesions - n (%)							
Yes	XX (XX.X)						
No	XX (XX.X)						
Number of New Lesions - n (%)							
1	XX (XX.X)						
2	XX (XX.X)						
...							
n	XX						
Mean (SD)	XX.XX (XX.XX)						
Median	XX.XX						
Min; Max	XX.X; XX.X						

*Programming Note: Repeat for  
all available assessments*

Program: (Program name.sas) (run on: DDMMYYYY HH:MM)

Filename: (Specify file name.rtf)

**Sponsor:** BioMed Valley Discoveries

**Protocol:** BVD-523-ABC

**Statistical Analysis Plan:**

2.0 / 09-Jun-2023

Table 14.2-1.3.2 – Incidence of New Lesions  
Per Protocol Set

**PROGRAMMING NOTES:**

- Repeat Table 14.2-1.3.1
- Present data on Per Protocol Set.
- For Part B only

Table 14.2-1.3.3 – Incidence of New Lesions  
Evaluable Analysis Set

**PROGRAMMING NOTES:**

- Repeat Table 14.2-1.3.1
- Present data on Evaluable Analysis Set.

Table 14.2-1.4.1 - Duration of Response  
Full Analysis Set

	Group 1 N=XX	Group 2 N=XX	Group 3 N=XX	Group 4 N=XX	Group 5 N=XX	Group 6 N=XX	Overall N=XX
Patients with response (CR+PR) - n (%)	XX (XX.X)						
Patients with events - n (%) [a]	XX (XX.X)						
Patients censored - n (%) [a]	XX (XX.X)						
Duration of response (months) [b]							
Median (95% CI)	XX (X.X, X.X)						
Min, Max	XX, XX*	XX, XX	XX, XX	XX, XX*	XX, XX	XX, XX*	XX, XX
KM probability estimates for duration of response (95% CI) [c]							
3 Months	XX (X.X, X.X)						
6 Months	XX (X.X, X.X)						
9 Months	XX (X.X, X.X)						
12 Months	XX (X.X, X.X)						
18 Months	XX (X.X, X.X)						

Note: CI=Confidence Interval, CR=Complete Response, PR=Partial Response.

Duration of response is the period from the date of initial PR or CR until the date of first radiographically documented progressive disease or death from any cause.

[a] Percentage calculated on patients with response. Events are death or disease progression.

[b] Product-limit (Kaplan-Meier) estimates. 95% CI for median calculated using the Brookmeyer and Crowley method.

[c] Based upon Kaplan-Meier (KM) estimates and 95% CI use the log-log transformation.

\* Censored observation at maximum value.

Program: (Program name.sas) (run on: DDMMYYYY HH:MM)

Filename: (Specify file name.rtf)

**Sponsor:** BioMed Valley Discoveries

**Protocol:** BVD-523-ABC

**Statistical Analysis Plan:**

2.0 / 09-Jun-2023

Table 14.2-1.4.2 – Duration of Response  
Per Protocol Set

**PROGRAMMING NOTES:**

- Repeat Table 14.2-1.4.1
- Present data on Per Protocol Set.
- For Part B only

Table 14.2-1.4.3 – Duration of Response  
Evaluable Analysis Set

**PROGRAMMING NOTES:**

- Repeat Table 14.2-1.4.1
- Present data on Evaluable Analysis Set.

Table 14.2-1.5.1 - Progression-Free Survival (PFS)  
Full Analysis Set

	Group 1 N=XX	Group 2 N=XX	Group 3 N=XX	Group 4 N=XX	Group 5 N=XX	Group 6 N=XX	Overall N=XX
Patients with events - n (%)	XX (XX.X)	XX (XX.X)	XX (XX.X)	XX (XX.X)	XX (XX.X)	XX (XX.X)	XX (XX.X)
Patients censored - n (%)	XX (XX.X)	XX (XX.X)	XX (XX.X)	XX (XX.X)	XX (XX.X)	XX (XX.X)	XX (XX.X)
PFS (months) [a]							
Median (95% CI)	XX (X.X, X.X) (X.X, X.X)	XX (X.X, X.X)	XX (X.X, X.X)	XX (X.X, X.X)	XX (X.X, X.X)	XX (X.X, X.X)	XX (X.X, X.X)
Min, Max	XX, XX* XX, XX	XX, XX	XX, XX	XX, XX* XX, XX	XX, XX	XX, XX* XX, XX	XX, XX
KM probability estimates for PFS (95% CI) [b]							
3 Months	XX (X.X, X.X)	XX (X.X, X.X)	XX (X.X, X.X)	XX (X.X, X.X)	XX (X.X, X.X)	XX (X.X, X.X)	XX (X.X, X.X)
6 Months	XX (X.X, X.X)	XX (X.X, X.X)	XX (X.X, X.X)	XX (X.X, X.X)	XX (X.X, X.X)	XX (X.X, X.X)	XX (X.X, X.X)
9 Months	XX (X.X, X.X)	XX (X.X, X.X)	XX (X.X, X.X)	XX (X.X, X.X)	XX (X.X, X.X)	XX (X.X, X.X)	XX (X.X, X.X)
12 Months	XX (X.X, X.X)	XX (X.X, X.X)	XX (X.X, X.X)	XX (X.X, X.X)	XX (X.X, X.X)	XX (X.X, X.X)	XX (X.X, X.X)
18 Months	XX (X.X, X.X)	XX (X.X, X.X)	XX (X.X, X.X)	XX (X.X, X.X)	XX (X.X, X.X)	XX (X.X, X.X)	XX (X.X, X.X)

Note: CI=Confidence Interval.

Progression-Free Survival (PFS) is the time from the first ulixertinibdose until the first radiographically documented progression of disease or death from any cause, whichever occurs first.

[a] Product-limit (Kaplan-Meier) estimates. 95% CI for median calculated using the Brookmeyer and Crowley method.

[b] Based upon Kaplan-Meier (KM) estimates and 95% CI use the log-log transformation.

\* Censored observation at maximum value.

Program: (Program name.sas) (run on: DDMMYYYY HH:MM)

Filename: (Specify file name.rtf)

**Sponsor:** BioMed Valley Discoveries

**Protocol:** BVD-523-ABC

**Statistical Analysis Plan:**

2.0 / 09-Jun-2023

Table 14.2-1.5.2 – Progression-Free Survival (PFS)  
Per Protocol Set

**PROGRAMMING NOTES:**

- Repeat Table 14.2-1.5.1
- Present data on Per Protocol Set.
- For Part B only

Table 14.2-1.5.3 – Progression-Free Survival (PFS)  
Evaluable Analysis Set

**PROGRAMMING NOTES:**

- Repeat Table 14.2-1.5.1
- Present data on Evaluable Analysis Set.

Table 14.2-1.6.1 - Overall Survival (OS)  
Full Analysis Set

	Group 1 N=XX n (%)	Group 2 N=XX n (%)	Group 3 N=XX n (%)	Group 4 N=XX n (%)	Group 5 N=XX n (%)	Group 6 N=XX n (%)	Overall N=XX n (%)
Patients with events - n (%)	XX (XX.X)	XX (XX.X)	XX (XX.X)	XX (XX.X)	XX (XX.X)	XX (XX.X)	XX (XX.X)
Patients censored - n (%)	XX (XX.X)	XX (XX.X)	XX (XX.X)	XX (XX.X)	XX (XX.X)	XX (XX.X)	XX (XX.X)
OS (months) [a]							
Median (95% CI)	XX (X.X, X.X) (X.X, X.X)	XX (X.X, X.X)	XX (X.X, X.X)	XX (X.X, X.X)	XX (X.X, X.X)	XX (X.X, X.X)	XX (X.X, X.X)
Min, Max	XX, XX*	XX, XX	XX, XX	XX, XX*	XX, XX	XX, XX*	XX, XX
KM probability estimates for PFS (95% CI) [b]							
3 Months	XX (X.X, X.X)	XX (X.X, X.X)	XX (X.X, X.X)	XX (X.X, X.X)	XX (X.X, X.X)	XX (X.X, X.X)	XX (X.X, X.X)
6 Months	XX (X.X, X.X)	XX (X.X, X.X)	XX (X.X, X.X)	XX (X.X, X.X)	XX (X.X, X.X)	XX (X.X, X.X)	XX (X.X, X.X)
9 Months	XX (X.X, X.X)	XX (X.X, X.X)	XX (X.X, X.X)	XX (X.X, X.X)	XX (X.X, X.X)	XX (X.X, X.X)	XX (X.X, X.X)
12 Months	XX (X.X, X.X)	XX (X.X, X.X)	XX (X.X, X.X)	XX (X.X, X.X)	XX (X.X, X.X)	XX (X.X, X.X)	XX (X.X, X.X)
18 Months	XX (X.X, X.X)	XX (X.X, X.X)	XX (X.X, X.X)	XX (X.X, X.X)	XX (X.X, X.X)	XX (X.X, X.X)	XX (X.X, X.X)

Note: CI=Confidence Interval.

Overall Survival (OS) is the time from the first ulixertinib dose until death from any cause.

[a] Product-limit (Kaplan-Meier) estimates. 95% CI for median calculated using the Brookmeyer and Crowley method.

[b] Based upon Kaplan-Meier (KM) estimates and 95% CI use the log-log transformation.

\* Censored observation at maximum value.

Program: (Program name.sas) (run on: DDMMYYYY HH:MM)

Filename: (Specify file name.rtf)

**Sponsor:** BioMed Valley Discoveries

**Protocol:** BVD-523-ABC

**Statistical Analysis Plan:**

2.0 / 09-Jun-2023

Table 14.2-1.6.2 – Overall Survival (OS)  
Per Protocol Set

**PROGRAMMING NOTES:**

- Repeat Table 14.2-1.6.1
- Present data on Per Protocol Set.
- For Part B only

Table 14.2-1.6.3 – Overall Survival (OS)  
Evaluable Analysis Set

**PROGRAMMING NOTES:**

- Repeat Table 14.2-1.6.1
- Present data on Evaluable Analysis Set.

Table 14.3-1.1 - Overview Summary of Treatment-Emergent Adverse Events  
Safety Analysis Set

	Group 1 N=XX n (%)	Group 2 N=XX n (%)	Group 3 N=XX n (%)	Group 4 N=XX n (%)	Group 5 N=XX n (%)	Group 6 N=XX n (%)	Overall N=XX n (%)
Number of patients with:							
Any TEAE	XX (XX.X)						
Any Related TEAE	XX (XX.X)						
Any SAE	XX (XX.X)						
Any Related SAE	XX (XX.X)						
Any TEAE leading to treatment discontinuation	XX (XX.X)						
Any Related TEAE leading to treatment discontinuation	XX (XX.X)						
Any TEAE leading to treatment discontinuation within 1 cycle	XX (XX.X)						
Any Related TEAE leading to treatment discontinuation within 1 cycle	XX (XX.X)						
Any TEAE leading to treatment discontinuation following 1 cycle	XX (XX.X)						
Any Related TEAE leading to treatment discontinuation following 1 cycle	XX (XX.X)						
Any TEAE leading to treatment interruption	XX (XX.X)						
Any Related TEAE leading to treatment interruption	XX (XX.X)						
Any TEAE leading to treatment interruption within 1 cycle	XX (XX.X)						
Any Related TEAE leading to treatment interruption within 1 cycle	XX (XX.X)						
Any TEAE leading to treatment interruption following 1 cycle	XX (XX.X)						
Any Related TEAE leading to treatment interruption following 1 cycle	XX (XX.X)						

Note: SAE=Serious Adverse Events, TEAE=Treatment-Emergent Adverse Events

Program: (Program name.sas) (run on: DDMMYYYY HH:MM)

Filename: (Specify file name.rtf)

Table 14.3-1.1 - Overview Summary of Treatment-Emergent Adverse Events  
Safety Analysis Set

	Group 1 N=XX n (%)	Group 2 N=XX n (%)	Group 3 N=XX n (%)	Group 4 N=XX n (%)	Group 5 N=XX n (%)	Group 6 N=XX n (%)	Overall N=XX n (%)
Number of patients with:							
Any TEAE leading to dose reduction	XX (XX.X)						
Any related TEAE leading to dose reduction	XX (XX.X)						
Any TEAE leading to dose reduction within Cycle 1	XX (XX.X)						
Any Related TEAE leading to dose reduction within Cycle 1	XX (XX.X)						
Any TEAE leading to dose reduction following Cycle 1	XX (XX.X)						
Any Related TEAE leading to dose reduction following Cycle 1	XX (XX.X)						
Any TEAE leading to death	XX (XX.X)						
Any Related TEAE leading to death	XX (XX.X)						
Any TEAE with Grade >= 3	XX (XX.X)						
Any Related TEAE with Grade >= 3	XX (XX.X)						

Note: SAE=Serious Adverse Events, TEAE=Treatment-Emergent Adverse Events

Program: (Program name.sas) (run on: DDMMYYYY HH:MM)

Filename: (Specify file name.rtf)

Table 14.3-1.2 - Summary of Treatment-Emergent Adverse Events by System Organ Class and Preferred Term  
Safety Analysis Set

System Organ Class Preferred Term	Group 1 N=XX n (%)	Group 2 N=XX n (%)	Group 3 N=XX n (%)	Group 4 N=XX n (%)	Group 5 N=XX n (%)	Group 6 N=XX n (%)	Overall N=XX n (%)
Any TEAE	XX (XX.X)						
System organ class 1	XX (XX.X)						
Preferred term 1	XX (XX.X)						
Preferred term 2	XX (XX.X)						
.....	XX (XX.X)						
System organ class 2	XX (XX.X)						
Preferred term 1	XX (XX.X)						
Preferred term 2	XX (XX.X)						
.....	XX (XX.X)						

Note: MedDRA <vx.x>. TEAE=Treatment-Emergent Adverse Events.

If there is more than one TEAE within a system organ class (SOC), the patient is counted only once under that SOC. If there is more than one TEAE within a SOC and preferred term (PT), the patient is counted only once in that SOC and PT.

Primary SOCs are presented by descending order of frequency for the overall group, PTs are sorted by descending order of frequency for the overall group within each SOC.

Program: (Program name.sas) (run on: DDMMYYYY HH:MM)

Filename: (Specify file name.rtf)

**Sponsor:** BioMed Valley Discoveries**Protocol:** BVD-523-ABC**Statistical Analysis Plan:**

2.0 / 09-Jun-2023

Table 14.3-1.3 – Summary of Related Treatment-emergent Adverse Events by System Organ Class and Preferred Term Safety Analysis Set

**PROGRAMMING NOTES:**

- Repeat Table 14.3-1.2
- Present Related TEAE: TEAEs with causality=Related, Possibly Related or missing.
- Add footnote:  
“Related TEAE: TEAEs with causality=Related, Possibly Related or missing.”

Table 14.3-1.4 – Summary of Serious Treatment-emergent Adverse Events by System Organ Class and Preferred Term Safety Analysis Set

**PROGRAMMING NOTES:**

- Repeat Table 14.3-1.2
- Present Serious TEAE: TEAEs with SAE =” Yes”.
- Add footnote:  
“Serious TEAE: TEAEs with SAE =” Yes”.”

Table 14.3-1.5 – Summary of Related Serious Treatment-emergent Adverse Events by System Organ Class and Preferred Term Safety Analysis Set

**PROGRAMMING NOTES:**

- Repeat Table 14.3-1.2
- Present Related Serious TEAE: SAEs with causality=Related, Possibly Related or missing.
- Add footnote:  
“SAEs with causality=Related, Possibly Related or missing.”

**Sponsor:** BioMed Valley Discoveries

**Protocol:** BVD-523-ABC

**Statistical Analysis Plan:**

2.0 / 09-Jun-2023

BioMed Valley Discoveries  
 Protocol: BVD-523-ABC ('Delivery' / 'Type') - Part X  
 Data extraction date: DDMMYYYY

Page 1 of Y

Table 14.3-1.6 - Summary of Treatment-Emergent Adverse Events by Preferred Term  
 Safety Analysis Set

System Organ Class Preferred Term	Group 1 N=XX n (%)	Group 2 N=XX n (%)	Group 3 N=XX n (%)	Group 4 N=XX n (%)	Group 5 N=XX n (%)	Group 6 N=XX n (%)	Overall N=XX n (%)
Any TEAE	XX (XX.X)						
Preferred term 1	XX (XX.X)						
Preferred term 2	XX (XX.X)						
.....							

Note: MedDRA <vx.x>. TEAE=Treatment-Emergent Adverse Events.

If there is more than one TEAE within a preferred term (PT), the patient is counted only once in that PT.

PTs are sorted in descending order of frequency for the overall group.

Program: (Program name.sas) (run on: DDMMYYYY HH:MM)

Filename: (Specify file name.rtf)

**Sponsor:** BioMed Valley Discoveries**Protocol:** BVD-523-ABC**Statistical Analysis Plan:**

2.0 / 09-Jun-2023

Table 14.3-1.7 – Summary of Related Treatment-emergent Adverse Events by Preferred Term  
Safety Analysis Set

**PROGRAMMING NOTES:**

- Repeat Table 14.3-1.6
- Present Related TEAE: TEAEs with causality=Related, Possibly Related or missing.
- Add footnote:  
“Related TEAE: TEAEs with causality=Related, Possibly Related or missing.”

Table 14.3-1.8 – Summary of Serious Treatment-emergent Adverse Events by Preferred Term  
Safety Analysis Set

**PROGRAMMING NOTES:**

- Repeat Table 14.3-1.6
- Present Serious TEAE: TEAEs with SAE =” Yes”.
- Add footnote:  
“Serious TEAE: TEAEs with SAE =” Yes”.”

Table 14.3-1.9 – Summary of Related Serious Treatment-emergent Adverse Events by Preferred Term  
Safety Analysis Set

**PROGRAMMING NOTES:**

- Repeat Table 14.3-1.6
- Present Related Serious TEAE: SAEs with causality=Related, Possibly Related or missing.
- Add footnote:  
“SAEs with causality=Related, Possibly Related or missing.”

Table 14.3-1.10 - Summary of Treatment-Emergent Adverse Events by System Organ Class and Preferred Term for Maximum CTCAE Grade Safety Analysis Set

Group: Group X

System Organ Class Preferred Term	Any CTC Grade n (%) [Events]	CTC Grade 1 n (%)	CTC Grade 2 n (%)	CTC Grade 3 n (%)	CTC Grade 4 n (%)	CTC Grade 5 n (%)
Any TEAE	XX (XX.X) [XX]	XX (XX.X)				
System organ class 1						
Preferred term 1	XX (XX.X) [XX]	XX (XX.X)				
Preferred term 2	XX (XX.X) [XX]	XX (XX.X)				
.....	XX (XX.X) [XX]	XX (XX.X)				
System organ class 2						
Preferred term 1	XX (XX.X) [XX]	XX (XX.X)				
Preferred term 2	XX (XX.X) [XX]	XX (XX.X)				
.....	XX (XX.X) [XX]	XX (XX.X)				

Note: MedDRA <vx.x>; CTCAE v5.0. TEAE=Treatment-Emergent Adverse Events.

If there is more than one TEAE within a system organ class (SOC), the patient is counted only once under that SOC and maximum severity. If there is more than one TEAE within a SOC and preferred term (PT), the patient is counted only once in that SOC, PT and maximum severity. Primary SOCs are presented by descending order of frequency for the overall group, PTs are sorted within primary SOC descending order of frequency for the overall group within each SOC.

[Events] presents the number of TEAEs reported overall, by primary SOC and PT regardless of severity.

Program: (Program name.sas) (run on: DDMMYYYY HH:MM)

Filename: (Specify file name.rtf)

**PROGRAMMING NOTES:**

- Present for each group and overall.

**Sponsor:** BioMed Valley Discoveries

**Protocol:** BVD-523-ABC

**Statistical Analysis Plan:**

2.0 / 09-Jun-2023

Table 14.3-1.11 – Summary of Related Treatment-Emergent Adverse Events by System Organ Class and Preferred Term  
for Maximum CTCAE Grade  
Safety Analysis Set

**PROGRAMMING NOTES:**

- Repeat Table 14.3-1.10
- Present Related TEAE: TEAEs with causality=Related, Possibly Related or missing.
- Add footnote:  
“Related TEAE: TEAEs with causality=Related, Possibly Related or missing.”

Table 14.3-1.12 - Summary of Treatment-Emergent Adverse Events Leading to Treatment Discontinuation  
by System Organ Class and Preferred Term  
Safety Analysis Set

System Organ Class Preferred Term	Group 1 N=XX n (%)	Group 2 N=XX n (%)	Group 3 N=XX n (%)	Group 4 N=XX n (%)	Group 5 N=XX n (%)	Group 6 N=XX n (%)	Overall N=XX n (%)
Any TEAE leading to treatment discontinuation	XX (XX.X)						
System organ class 1	XX (XX.X)						
Preferred term 1	XX (XX.X)						
Preferred term 2	XX (XX.X)						
.....	XX (XX.X)						
System organ class 2	XX (XX.X)						
Preferred term 1	XX (XX.X)						
Preferred term 2	XX (XX.X)						
.....	XX (XX.X)						

Note: MedDRA <vx.x>. TEAE=Treatment-Emergent Adverse Events.

If there is more than one TEAE leading to treatment discontinuation within a system organ class (SOC), the patient is counted only once under that SOC. If there is more than one TEAE leading to treatment discontinuation within a SOC and preferred term (PT), the patient is counted only once in that SOC and PT.

Primary SOCs are presented by descending order of frequency for the overall group, PTs are sorted within primary SOC descending order of frequency for the overall group within each SOC.

TEAEs leading to treatment discontinuation: any TEAEs with Action taken with study treatment=Drug withdrawn.

Program: (Program name.sas) (run on: DDMMYYYY HH:MM)

Filename: (Specify file name.rtf)

**Sponsor:** BioMed Valley Discoveries**Protocol:** BVD-523-ABC**Statistical Analysis Plan:**

2.0 / 09-Jun-2023

Table 14.3-1.13 – Summary of Related Treatment-Emergent Adverse Events Leading to Treatment Discontinuation  
Safety Analysis Set

**PROGRAMMING NOTES:**

- Repeat Table 14.3-1.12
- Present Related TEAE: TEAEs with causality=Related, Possibly Related or missing.
- Add footnote:  
“Related TEAE: TEAEs with causality=Related, Possibly Related or missing.”

Table 14.3-1.14 – Summary of Treatment-Emergent Adverse Events Leading to Treatment Discontinuation Within Cycle 1  
Safety Analysis Set

**PROGRAMMING NOTES:**

- Repeat Table 14.3-1.12
- Add footnote:  
“TEAEs leading to treatment discontinuation: any TEAEs with Action taken with study treatment=Drug withdrawn within the first 28 days of study.”

Table 14.3-1.15 – Summary of Related Treatment-Emergent Adverse Events Leading to Treatment Discontinuation Within Cycle 1  
Safety Analysis Set

**PROGRAMMING NOTES:**

- Repeat Table 14.3-1.12
- Present Related TEAE: TEAEs with causality=Related, Possibly Related or missing.
- Add footnote:  
“TEAEs leading to treatment discontinuation: any TEAEs with Action taken with study treatment=Drug withdrawn within the first 28 days of study.”

**Sponsor:** BioMed Valley Discoveries

**Protocol:** BVD-523-ABC

**Statistical Analysis Plan:**

2.0 / 09-Jun-2023

Table 14.3-1.16 - Summary of Treatment-Emergent Adverse Events Leading to Treatment Discontinuation Following Cycle 1 Safety Analysis Set

**PROGRAMMING NOTES:**

- Repeat Table 14.3-1.12
- Add footnote:

“TEAEs leading to treatment discontinuation: any TEAEs with Action taken with study treatment=Drug withdrawn after the first 28 days of study.”

“Related TEAE: TEAEs with causality=Related, Possibly Related or missing.”

Table 14.3-1.17 - Summary of Related Treatment-Emergent Adverse Events Leading to Treatment Discontinuation Following Cycle 1 Safety Analysis Set

**PROGRAMMING NOTES:**

- Repeat Table 14.3-1.12

- Present Related TEAE: TEAEs with causality=Related, Possibly Related or missing.’

- Add footnote:

“TEAEs leading to treatment discontinuation: any TEAEs with Action taken with study treatment=Drug withdrawn after the first 28 days of study.”

“Related TEAE: TEAEs with causality=Related, Possibly Related or missing.”

**Sponsor:** BioMed Valley Discoveries

**Protocol:** BVD-523-ABC

**Statistical Analysis Plan:**

2.0 / 09-Jun-2023

Table 14.3-1.18 – Summary of Treatment-Emergent Adverse Events Leading to Treatment Interruption  
Safety Analysis Set

**PROGRAMMING NOTES:**

- Repeat Table 14.3-1.12
- Replace 'Any TEAE' by 'Any TEAE leading to treatment interruption.'
- Add footnote:  
"Includes TEAE with 'Action Taken with treatment' = 'Dose Interrupted'.

Table 14.3-1.19 – Summary of Related Treatment-Emergent Adverse Events Leading to Treatment Interruption  
Safety Analysis Set

**PROGRAMMING NOTES:**

- Repeat Table 14.3-1.12
- Replace 'Any TEAE' by 'Any related TEAE leading to treatment interruption.'
- Add footnotes:  
"Includes TEAE with 'Action Taken with treatment' = 'Dose Interrupted'.  
"Related TEAE: TEAEs with causality=Related, Possibly Related or missing."

**Sponsor:** BioMed Valley Discoveries**Protocol:** BVD-523-ABC**Statistical Analysis Plan:**

2.0 / 09-Jun-2023

Table 14.3-1.20 – Summary of Treatment-Emergent Adverse Events Leading to Treatment Interruption Within Cycle 1  
Safety Analysis Set

**PROGRAMMING NOTES:**

- Repeat Table 14.3-1.12
- Replace 'Any TEAE' by 'Any TEAE leading to treatment interruption within Cycle 1.'
- Add footnote:  
"Includes TEAE with 'Action Taken with treatment' = 'Dose Interrupted' within the first 28 days of study."

Table 14.3-1.21 – Summary of Related Treatment-Emergent Adverse Events Leading to Treatment Interruption Within Cycle 1  
Safety Analysis Set

**PROGRAMMING NOTES:**

- Repeat Table 14.3-1.12
- Replace 'Any TEAE' by 'Any related TEAE leading to treatment interruption within Cycle 1.'
- Add footnotes:  
"Includes TEAE with 'Action Taken with treatment' = 'Dose Interrupted' after the first 28 days of study."

**Sponsor:** BioMed Valley Discoveries

**Protocol:** BVD-523-ABC

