### 9.9.1 Adverse Events (AEs)

The following definitions will be used:

- **Treatment-emergent AEs (TEAEs):** Treatment-emergent adverse event (TEAE) is defined as any AE that emerges during on-treatment period, after the 1st dose of the study agent.
- **Related AEs:** AEs suspected by the Investigator and/or Sponsor to have a relationship to study treatment (as recorded on the AE eCRF page, Causality = Related, Possibly Related, or missing).
- **Serious Adverse Events (SAE):** serious AEs (as recorded on the AE eCRF page, Does AE Meet the Definition of an SAE = Yes).
- **AEs leading to treatment discontinuation:** AEs leading to permanent discontinuation of study treatment (as recorded on the AE eCRF page, Action taken with study treatment = Drug withdrawn).
- **AEs leading to dose reduction:** AEs leading to dose reduction of study treatment (as recorded on the AE eCRF page, Action taken with study treatment = Dose Reduced).
- **AEs leading to treatment interruption:** AEs leading to treatment interruption of study treatment (as recorded on the AE eCRF page, Action taken with study treatment = Drug Interrupted).
- **AEs leading to Death:** adverse event leading to death (as recorded on the AE eCRF page, Results in death, or Outcome = Fatal, or Grade = 5).

An overview summary table will present the number and percentage of patients with a TEAE, including:

- TEAEs / TEAEs related to study treatment

- SAEs / SAEs related to study treatment
- TEAEs leading to treatment discontinuation / TEAEs related to study treatment leading to treatment discontinuation
- TEAEs leading to treatment discontinuation within 1 cycle / TEAEs related to study treatment leading to treatment discontinuation within 1 cycle
- TEAEs leading to treatment discontinuation following 1 cycle / TEAEs related to study treatment leading to treatment discontinuation following 1 cycle
- TEAEs leading to treatment interruption / TEAEs related to study treatment leading to treatment interruption
- TEAEs leading to treatment interruption within 1 cycle / TEAEs related to study treatment leading to treatment interruption within 1 cycle
- TEAEs leading to treatment interruption following 1 cycle / TEAEs related to study treatment leading to treatment interruption following 1 cycle
- TEAEs leading to dose reduction / TEAEs related to study treatment leading to dose reduction

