**Statistical Analysis Plan:**

2.0 / 09-Jun-2023

Table 14.3-1.22 – Summary of Related Treatment-Emergent Adverse Events Leading to Treatment Interruption Following Cycle 1  
Safety Analysis Set

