**PROGRAMMING NOTES:**

- Repeat Table 14.3-1.12
- Replace 'Any TEAE' by 'Any TEAE leading to treatment interruption following Cycle 1.'
- Add footnote:  
"Includes TEAE with 'Action Taken with treatment' = 'Dose Interrupted' after the first 28 days of study.  
"Related TEAE: TEAEs with causality=Related, Possibly Related or missing."

Table 14.3-1.23 – Summary of Related Treatment-Emergent Adverse Events Leading to Treatment Interruption Following Cycle 1  
Safety Analysis Set

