**PROGRAMMING NOTES:**

- Repeat Table 14.3-1.20
- Present Related TEAE: TEAEs with causality=Related, Possibly Related or missing.
- Add footnote:  
“Related TEAE: TEAEs with causality=Related, Possibly Related or missing.”

Table 14.3-1.32 - Summary of Deaths  
All Patients Set

	Group 1 N=XX n (%)	Group 2 N=XX n (%)	Group 3 N=XX n (%)	Group 4 N=XX n (%)	Group 5 N=XX n (%)	Group 6 N=XX n (%)	Screen Failures N=XX n (%)	Overall N=XX n (%)
Patients who died during the study	XX (XX.X)	XX (XX.X)						
Primary cause of death								
Progressive Disease	XX (XX.X)	XX (XX.X)						
Adverse Event	XX (XX.X)	XX (XX.X)						
Unknown	XX (XX.X)	XX (XX.X)						
Patients who died after taking the first dose of ulixertinib	XX (XX.X)	XX (XX.X)						
Primary cause of death								
Progressive Disease	XX (XX.X)	XX (XX.X)						
Adverse Event	XX (XX.X)	XX (XX.X)						
Unknown	XX (XX.X)	XX (XX.X)						

Program: (Program name.sas) (run on: DDMMYYYY HH:MM)

Filename: (Specify file name.rtf)

Table 14.3-2.1 - Summary and Change from Baseline in Hematology Laboratory Results by Visit Safety Analysis Set

Parameter: XXXXX (XX)	Group 1 N=XX	Group 2 N=XX	Group 3 N=XX	Group 4 N=XX	Group 5 N=XX	Group 6 N=XX	Overall N=XX
Baseline							
n	XX						
Mean (SD)	XX.X (XX.XX)						
Median	XX.X						
Min; Max	XX; XX						
C1D8							
n	XX						
Mean (SD)	XX.X (XX.XX)						
Median	XX.X						
Min; Max	XX; XX						
Change from Baseline to C1D8							
n	XX						
Mean (SD)	XX.X (XX.XX)						
Median	XX.X						
Min; Max	XX; XX						

Note: Baseline is the last available assessment prior to first dose of study treatment.

Program: (Program name.sas) (run on: DDMMYYYY HH:MM)

Filename: (Specify file name.rtf)

**Sponsor:** BioMed Valley Discoveries

**Protocol:** BVD-523-ABC

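### Three safety table shells marked for the final analysis (14.3-1.21, 14.3-1.22 and 14.3-1.31) have titles and programming notes that contradict each other

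*SAP*

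**What the plan says.** SAP 7.2 states that, because the study stopped early during Part A, the report will be shortened and will concentrate on safety. The list of tables, figures and listings marks the outputs to be delivered with a Y. Tables 14.3-1.16, 14.3-1.18 to 14.3-1.23 and 14.3-1.31 are all marked.

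- **Table 14.3-1.21.** The shell title is "Summary of Related Treatment-Emergent Adverse Events Leading to Treatment Interruption Within Cycle 1" and the row label is "Any related TEAE leading to treatment interruption within Cycle 1". The footnote to be added gives the inclusion rule as "Dose Interrupted' after the first 28 days of study".
- **Table 14.3-1.22.** The list of outputs has this as the all-cause table for the period after Cycle 1. The shell title is "Summary of Related Treatment-Emergent Adverse Events Leading to Treatment Interruption Following Cycle 1". The note on the row label says "Replace 'Any TEAE' by 'Any TEAE leading to treatment interruption following Cycle 1", which is all-cause. A footnote defining related events is also added.
- **Table 14.3-1.31.** The title is for related events leading to death. The first programming note is "Repeat Table 14.3-1.20", and that table shows interruptions within Cycle 1.
- **Action-taken value.** SAP 9.9.1 defines interruption, as recorded on the adverse event eCRF page, by "Action taken with study treatment = Drug Interrupted". The interruption shells write Dose where SAP 9.9.1 writes Drug.

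**The concern.** The shells are the working specification for the programmer and for whoever checks the output, and their titles and footnotes are printed in the report. When a title and an inclusion footnote name opposite time windows, one of two things happens. Either the wrong records are shown, or the right records are shown under a rule that does not describe them.

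The tables concerned show which events, by system organ class and preferred term, led to interruption early or late in treatment and were judged drug-related. The fourth item is the table of drug-related deaths. In a report narrowed to safety, a reader relies on these tables being labelled correctly. The shells are at version 2.0, already updated after dry-run comments, and the contradictions remain.

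**Working it through.** No power, alpha or event count bears on this point. The check sets the list of outputs, the shell titles, the row labels and the notes side by side.

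| Table | List of outputs | Shell title | Row label | Rule or parent in the notes |
|---|---|---|---|---|
| 14.3-1.20 | all-cause, within Cycle 1 | all-cause, within | all-cause, within | within 28 days |
| 14.3-1.21 | related, within Cycle 1 | related, within | related, within | **after 28 days**; no related-event footnote |
| 14.3-1.22 | all-cause, following Cycle 1 | **related**, following | all-cause, following | after 28 days; **related-event footnote** |
| 14.3-1.23 | related, following Cycle 1 | related, following | related, following | after 28 days; related-event footnote |
| 14.3-1.31 | related, death | related, death | none given, so inherited | **parent is 14.3-1.20** |

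**Table 14.3-1.21.** The schedule of activities (SAP 14.1) sets Cycle 1 as Days 1 to 28. The footnote admits Day 29 onward, so the two windows do not overlap. Its all-cause counterpart, 14.3-1.20, uses "Dose Interrupted' within the first 28 days of study". Twelve shells split discontinuation, interruption or dose reduction at Cycle 1: 14.3-1.14 to 1.17, 1.20 to 1.23 and 1.26 to 1.29. In eleven of them the window agrees with the title, and 14.3-1.21 is the only exception. No other convention explains it.

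Following the row label (related) together with the footnote (after 28 days) gives exactly the population of 14.3-1.23. As an illustration, assume that event and interruption fall on the same day. A patient whose only related interruption is on day 10 would be missing from 14.3-1.21, and one whose only related interruption is on day 60 would appear there. Both results would conflict with the rows in overview Table 14.3-1.1 for related interruptions within one cycle. Unlike 14.3-1.19 and 14.3-1.23, this shell also lacks the footnote defining related events.

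**Table 14.3-1.22.** The list entry and the row label agree on all-cause, and the window is right. The title and the extra footnote disagree with both. The shell title is word for word that of 14.3-1.23, so two outputs share one title.

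**Table 14.3-1.31.** Table 14.3-1.20 carries an interruption row label and an interruption footnote. The notes for 14.3-1.31 replace neither. They only restrict to related events and add the footnote for that restriction. The death rule (resulting in death, fatal outcome or Grade 5) is in 14.3-1.30, which is not the parent named.

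**Table 14.3-1.16.** This all-cause table on discontinuation after Cycle 1 also carries the related-event footnote, which has no use there.

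**The case against.** The strongest case on the other side is that these are proofreading slips which would not mislead a competent programmer. For 14.3-1.21, the list of outputs, the shell title and the row label all say related and within Cycle 1, and only one footnote says otherwise. For 14.3-1.22, nothing instructs the programmer to restrict to related events. Other shells, such as 14.3-1.3 and 14.3-1.13, do that with a separate note, and here it is absent. For 14.3-1.31, the title and the causality note are right and only a table number is wrong. The related interruption counts by period are correctly specified in Table 14.3-1.1. Listing 16.2.7-2 shows onset day, relatedness and action taken, and Listing 16.2.5-2 shows interruption dates and reasons. All three are in the final delivery, so a misbuilt table should be caught and no information would be lost.

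Most of this stands as a limit on the harm. It does not remove the point, because the footnotes and titles are printed. A correctly programmed 14.3-1.21 would still state a false rule, and 14.3-1.22 would still be titled as related.

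Three stronger readings are tempting but not supported:

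- A reader might infer that every record in 14.3-1.21 will be wrong. That follows only if the footnote is obeyed against three consistent labels.
- A reader might infer that all six interruption tables will come out empty because the shells say Dose Interrupted and SAP 9.9.1 says Drug Interrupted. The shells also paraphrase the field name, which suggests display wording, and the eCRF is not among the documents.
- A reader might infer that the Cycle 1 split is the plan's declared test of starting-dose tolerability. The documents do not say so. The protocol gives review of starting-dose toleration to the Safety Monitoring Committee, whose outputs are covered by a separate SAP.

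**Conclusion.** The contradictions are real and can be read directly from the text. Three shells are affected (14.3-1.21, 14.3-1.22 and 14.3-1.31), and 14.3-1.16 has a stray footnote.

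- In 14.3-1.21 the window is reversed. The result is a duplicate of 14.3-1.23 if the footnote is followed, and a false printed rule if it is not.
- 14.3-1.22 is a labelling contradiction, not a demonstrated error of selection.
- 14.3-1.31 has a wrong cross-reference.

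The difference between Dose and Drug Interrupted is a minor point of harmonisation. The footnotes do not say whether the 28 days are counted to event onset or to the interruption itself, so the example above rests on the two coinciding. No efficacy endpoint, analysis set or sample size is touched. The corrections should be made because these tables belong to a report centred on safety and cost almost nothing to put right.

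**What to change.** - **14.3-1.21:** change 'after' to 'within' in the inclusion footnote, to match 14.3-1.20, and add the related-event footnote used in 14.3-1.19 and 14.3-1.23.
- **14.3-1.22:** delete 'Related' from the shell title and remove the related-event footnote.
- **14.3-1.31:** change the parent table from 14.3-1.20 to 14.3-1.30.
- **14.3-1.16:** remove the related-event footnote.
- **14.3-1.18 to 14.3-1.23:** check the recorded value on the eCRF, then align the shell wording with SAP 9.9.1.

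The first four items edit four shells and the last edits six. Two shells are common to both, so 4 + 6 − 2 = 8 shells change. No new data or clinical judgement is needed. Whether programming is already complete cannot be told from the documents. If it is, the affected tables should be checked against Table 14.3-1.1 and Listing 16.2.7-2 and reissued where needed.
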